Version 11/1/2018 Study Protocol

Project Title: A Prospective Randomized Control Trial of Pilocarpine use After Combined Cataract/Trabectome Surgery

Principal Investigator: [name] MD

Co-investigators: [name] MD, PGY-2; [name] MD, PGY-3

Site(s) where study will be performed: Montefiore Medical Center, Ophthalmology Department

Background

Glaucoma is the leading cause of irreversible blindness worldwide, and its treatment consists of lowering intraocular pressure to prevent damage to the optic nerve and loss of vision[1]. Current methods for lowering intraocular pressure (IOP) include topical and oral medications, laser trabeculoplasty, microincisional glaucoma surgery (MIGS), and traditional incisional surgeries such as trabeculectomy and aqueous tube shunts. MIGS have become more popular in recent years as less invasive methods than traditional surgeries that effectively reduce IOP and help reduce the medication burden on patients[1]. There are multiple available MIGS procedures, most of which act by increasing trabecular outflow. One such procedure is the Trabectome, which is usually performed in combination with cataract surgery. Trabectome is an FDA approved device used to perform a trabeculectomy via an internal approach. A strip of 60-120 degrees of the nasal angle trabecular meshwork and the inner wall of Schlemm's canal are removed providing a direct pathway for aqueous outflow from the anterior chamber into the collector channels[2].

Pilocarpine, a parasympathomimetic agent, is a glaucoma medication that works by causing contraction of the ciliary muscle leading to opening of the trabecular meshwork[3]. Due to its frequent dosing requirement and large number of ocular and systemic side effects, pilocarpine has largely fallen out of favor for the treatment of primary open angle glaucoma (POAG), except in patients for whom few other alternatives exist. However, pilocarpine is often used after trabectome surgery. The rational for its use after Trabectome procedure is for its miotic effect, which theoretically may prevent the formation of peripheral anterior synechiae. Formation of peripheral anterior synechiae can lead to the closure of the cleft that is generated and the possibility of failure of the procedure. While the theoretical benefit of pilocarpine has been proposed, its actual benefit has never been proven. In this study, we aim to evaluate whether Trabecome / Cataract surgery without pilocarpine is non-inferior to Trabecome / Cataract surgery procedure followed by treatment with pilocarpine. The outcomes to be evaluated are the degree (percentage) of IOP lowering from baseline after the procedure, the mean post-operative IOP, the number of IOP lowering agents required to achieve goal IOP, and the rate of progression towards further glaucoma surgeries.

Key Questions

1. What are the demographics and characteristics of patients undergoing combined cataract/trabectome surgery at Montefiore Medical Center?
2. What is the post procedure percent IOP drop at 1 month, 6 months and 1 year after surgery.

3. What is the number of pre and post procedure drops required to achieve goal IOP at 6 months, 1, 2 and 3 years after combined cataract/trabectome surgery in patients treated with post-op pilocarpine vs control?
4. What is the rate of progression towards further surgery in patients treated with post-op pilocarpine vs control over a 3 year follow up period?
5. What is the rate of pilocarpine related side effects and drug discontinuation due to adverse effects?

Objectives

1. To determine whether Trabectome/cataract surgery without pilocarpine is non-inferior to Trabecome / Cataract surgery procedure followed by treatment with pilocarpine in decreasing IOP at 1 year after surgery.
2. To determine the incidence and characteristics of pilocarpine induced side effects in this population.

Selection of Patients

1. Inclusion Criteria: Patients with ocular hypertension or open angle glaucoma undergoing combined cataract surgery with trabectome in a single surgical center at Montefiore Medical Center with a single provider between March 1st 2018 and July 1st 2020
2. Exclusion Criteria: Patients with previous history of eye surgeries (including laser procedures).
3. Age Range: 30 to 100 years old

Study Design

Prospective randomized controlled trial

Study Methods

140 consecutive patients with POAG who are planned for combined cataract/trabectome surgeries will be consented for inclusion in this study. Patients will be randomized to one of two study arms, using an online computer randomizer; the first group labeled “treatment group” and the second “control group.” The treatment group will receive post-operative treatment with pilocarpine 2% for 1 month postoperatively, in addition to the standard post-operative surgical drops including topical steroids and topical antibiotic drops. The control group will receive the usual post-operative drop schedule without pilocarpine. Most surgeons who do combined trabectome/cataract surgery will include the use of pilocarpine besides steroid and antibiotic. However, it is also acceptable for patients to only receive steroid and antibiotics (without pilocarpine) after such surgery. Patients in both groups will be followed for 1 year with the primary endpoint of percent decrease in IOP after surgery at 1 year. Secondary outcome measures will include: progression of glaucoma on OCT and HVF testing, medication side effects, number of pre and postoperative drops the patient was using before and after surgery, and need for further glaucoma surgery. All subsequent visits will be according to routine post-operative monitoring, where visual acuities, intraocular pressures, gonioscopy measurements will be performed at the slit lamp. These visits will coincide with standard of care post op follow up visits.

Participant recruitment

140 consecutive patients with POAG who are planned for combined cataract/trabectome surgeries with the principal investigator will be consented for inclusion in this study. Patients will be given a copy of the consent document to read over and they will be given time to ask any questions they have about the study. Participation in the study is completely voluntary and if they do not wish to participate in the study they can continue their care with the principal investigator and undergo their combined cataract/trabectome surgery without any remediation and their information will not be used in the study.

Confidentiality of data

Electronic data will be saved under a password protected computer in an anonymized fashion. Only the co-investigators will have access to the data for the duration of the study and only the co-investigators will be able to add data to the database. The data will be destroyed at the completion of the study.

Consent

Patients will provide written consent prior to participation in the study, as obtained by the investigators of this study. Once eligible patients are identified for the procedure at the pre-op visit, they will be asked to fill out the informed consent form and all questions will be answered. Patients will be informed of all risks and benefits of both the procedure and the use of pilocarpine as outlined further below. As no placebo will be utilized, patients will not be blinded to which group they are in.

Risks and Benefits:

1. Risks: Potential risks include the proposed risk of failure of the trabectome surgery secondary to scarring in both groups. Additional risk includes side effects of the use of pilocarpine, including but not limiting to: blurry vision, decrease night vision, headaches, browache, nausea, vomiting, diarrhea.
2. Benefits: Patients - the benefit to not using pilocarpine is a decrease in the medication burden and a decrease in the potential side effects that can occur with pilocarpine use. Additional benefits include for society and for the investigators due to the knowledge that will be gained from the study.

Statistical Considerations

1. Proposed sample size: 140
2. Proposed time period to be evaluated: 1 year of follow up
3. Feasibility of study – Over the time period 2/2016 – 9/2017, [name] completed 118 combined cataract/trabectome surgeries. Based on her historical usage and her usage of the combined procedure only increasing due to its success, we believe 140 patients can be recruited over a 1.5 – 2 year time frame.

Analytic Plan

All analyses will be based on the intent-to-treat approach (ITT). Standard descriptive statistics will be used to summarize the baseline characteristics and outcomes of the two treatment arms. The primary endpoint, percent decrease in IOP at 1 year after surgery compared to baseline, will be analyzed by computing the mean difference of this endpoint between treatment groups (pilocarpine - no pilocarpine) along with the corresponding two-sided 95% confidence interval. Non-inferiority of treatment without pilocarpine will be declared if the upper limit of the two-sided confidence interval is less than the margin of non-inferiority, which is deemed to be 5% in this study. Since the ITT approach can be anti-conservative in non-inferiority trials, a per-protocol analysis will also be performed. Two sample tests of the standard null hypothesis of no difference between groups will be conducted using the student T-test

for continuous variables or chi-square test for categorical variables (e.g., occurrence of side effects, need for further surgery). Linear or logistic regression models will be fit to the data to adjust for any baseline characteristics which are found to differ between treatment arms. In addition, generalized linear mixed models will be fit to the repeated measures obtained post-surgery, as part of every standard clinic encounter during follow-up, to assess whether the longitudinal trends in the outcomes differ between groups.

Sample size considerations

The sample size for this study is 140 subjects (70 per group). This sample size will yield greater than 95% power at a 1-sided Type I error rate of 2.5% (two-sided of 5%) to declare non-inferiority of the no pilocarpine group to the pilocarpine group with respect to the percent decrease in IOP after surgery, assuming an alternative hypothesis of no difference between groups, a non-inferiority margin of 5%, and a SD of 7.5% in both groups based on prior studies.

Data and Safety Monitoring Policy

As pilocarpine is an FDA approved medication with the overall risk level to the patient deemed to be mild, DSM will be undertaken by the investigator. At each office visit over the course of the life of the study (all visits as part of standard of care) specific attention will be made to reviewing whether the patient is having any potential side effects of the medication. If any side effects are noted and either the side effect cannot be tolerated by the patient or it is deemed to not be safe for the patient to continue to use the medication, the medication will be stopped and the patients inclusion in the study terminated.

1. Hu, K., et al., *Ab interno trabecular bypass surgery with Trabectome for open angle glaucoma*. Cochrane Database Syst Rev, 2016(8): p. Cd011693.
2. Mizoguchi, T., et al., *Clinical results of Trabectome surgery for open-angle glaucoma*. Clin Ophthalmol, 2015. 9: p. 1889-94.
3. *Isotox Carpine (pilocarpine)[Package insert]*: Alcon, Inc. TX. 2010

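### The time at which the allocation is released is not stated, so the single surgeon could know the arm while operating, although the arm is not needed until surgery is over

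*Combined protocol and SAP*

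**What the plan says.** Study Methods describes the entry population as patients awaiting surgery: "140 consecutive patients with POAG who are planned for combined cataract/trabectome surgeries will be consented for inclusion in this study". The Consent section places consent before the operation: "Once eligible patients are identified for the procedure at the pre-op visit, they will be asked to fill out the informed consent form".

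The allocation step is given in Study Methods: "Patients will be randomized to one of two study arms, using an online computer randomizer". No section states when this occurs relative to surgery, who runs the tool, how the result is concealed, or whether the surgeon is kept unaware of it. The only statement on masking, under Consent, is that patients will know their group because there is no placebo.

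The randomised treatment begins after the operation: "The treatment group will receive post-operative treatment with pilocarpine 2% for 1 month postoperatively". The other arm receives the usual post-operative drops without it.

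The inclusion criteria restrict surgery to one centre and "with a single provider between March 1st 2018 and July 1st 2020". Participant recruitment identifies that surgeon as the principal investigator. The Background describes the device as removing "A strip of 60-120 degrees of the nasal angle trabecular meshwork". No section sets a standard extent for this trial or asks for the extent to be recorded.

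The Analytic Plan says "All analyses will be based on the intent-to-treat approach (ITT"), and adds a per-protocol analysis because intention-to-treat can be anti-conservative for non-inferiority. Neither set is defined further, and no rule covers a randomised patient whose combined procedure is changed or cancelled.

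**The concern.** The operation is shared by both arms and is intended to lower IOP, which is what the primary endpoint measures at 1 year. The Background also names closure of the surgical cleft as the failure that pilocarpine is supposed to prevent. A surgeon who knows that a patient will not receive pilocarpine could, without intending to, operate differently on that patient. If this favoured the no-pilocarpine arm, it would make non-inferiority easier to declare. The planned regression adjusts for baseline characteristics that differ between arms, so an unrecorded operative difference would not be adjusted for.

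A second consequence is conditional. If randomisation comes before surgery, patients whose trabectome is changed or not completed fall in the intention-to-treat set. Where they still contribute a 1-year value and show no effect of arm, they pull the estimated difference toward zero.

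Both routes can be closed, because the design does not need the arm to be known before the operation ends.

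**Working it through.** **Inputs from the plan** (Analytic Plan; Sample size considerations): 70 per arm, SD 7.5, margin 5 percentage points, one-sided 2.5%. The difference is pilocarpine minus no pilocarpine, and non-inferiority is declared if the upper 95% limit is below 5.

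**Inputs assumed here**: the operative shift *b* and the proportion *c* of changed procedures. The documents give neither, so ranges are shown.

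**Step 1: reproduce the stated power.**
SE = 7.5 × √(2/70) = 1.268.
At a true difference of 0, 5/1.268 = 3.944. Normal approximation: Φ(3.944 − 1.960) = 97.6%. Noncentral t with 138 df: 97.5%. Both agree with the stated figure of more than 95%.

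**Step 2: operative shift.** Let the true effect of omitting pilocarpine equal the margin, so that declaring non-inferiority is an error with nominal rate 2.5%. An operative shift *b* favouring no pilocarpine makes the expected difference 5 − *b*. The error is the probability that a noncentral t with 138 df and noncentrality *b*/SE exceeds 1.977.

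| Shift favouring no pilocarpine (points) | *b*/SE | One-sided error |
|---|---|---|
| −1 (favours pilocarpine) | −0.789 | 0.3% |
| 0 | 0 | 2.5% |
| 1 | 0.789 | 12.0% |
| 2 | 1.578 | 34.7% |

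**Step 3: changed procedures kept in the analysis.** Suppose a proportion *c* of each arm has a changed procedure, still contributes a 1-year value, has the same mean and SD as the rest, and shows no arm difference. A true difference of 5 among the others becomes 5(1 − *c*), so the shift is 5*c*.

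| *c* | Shift 5*c* | One-sided error |
|---|---|---|
| 2% | 0.10 | 3.0% |
| 5% | 0.25 | 3.9% |
| 10% | 0.50 | 5.8% |
| 15% | 0.75 | 8.5% |

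The equal-mean assumption matters. If these patients had an IOP fall 20 points smaller in both arms (also assumed), then at *c* = 10% the SD becomes √(7.5² + 0.1 × 0.9 × 20²) = 9.6 and the error is 4.9% instead of 5.8%.

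**Step 4: fully cancelled patients treated as missing.** With 70(1 − *c*) evaluable per arm, power (normal approximation) is 97.4%, 97.0%, 96.3% and 95.3% for *c* = 2%, 5%, 10% and 15%. It stays above 95% throughout, and there is no dilution.

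**The case against.** The strongest reply is that the documents are silent and not wrong. They time consent, not randomisation, at the pre-op visit. A reader might infer that randomisation takes place before surgery, but the text allows that without establishing it. This stands, and it makes the second consequence conditional.

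A reader might also infer that patients whose surgery is cancelled remain in the intention-to-treat analysis and dilute it. The documents do not support this. The endpoint is measured 1 year after surgery and the inclusion criterion refers to patients undergoing the operation, so a fully cancelled patient would more naturally have no value at all (Step 4). Dilution is plausible only for a changed or incomplete procedure. The planned per-protocol analysis is a recognised response to that, though only a partial one: its set is undefined, and it cannot remove bias from a surgeon who knew the arm.

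Third, the 60 to 120 degree range is a Background description of the device. It is not an operative instruction for this trial, and it does not show that this surgeon varies the extent from patient to patient. Nothing in the documents links degrees ablated to IOP. The 1- and 2-point shifts therefore have no documentary basis, and bias in the other direction would make the test conservative. This also stands, so the figures show sensitivity and do not predict a bias. Having a single surgeon removes between-surgeon variation, but it does not stop that surgeon from knowing the arm.

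**Conclusion.** The concern holds in a limited form. Nothing in the documents prevents the operating principal investigator from knowing the arm before or during surgery, and the design gives no reason to allow it. That is an avoidable route to performance bias. It is more than a reporting gap, because the remedy changes how the trial is conducted. Dilution of the intention-to-treat comparison is a secondary risk that arises only if randomisation precedes surgery, and then mainly for changed or incomplete procedures.

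On assumed inputs, with the true difference at the margin, the one-sided error moves from 2.5% to 12% or 35% for an operative shift of 1 or 2 points favouring no pilocarpine, and to 0.3% for 1 point the other way. For 2% to 15% changed procedures it is 3.0% to 8.5%. The sensitivity arises because the standard error is only 1.27 points on the plan's SD. No stated figure is wrong, and the sample-size calculation reproduces. The documents do not show that allocation is in fact known at surgery or that the arms would be operated on differently. This is a cheap improvement that should be made.

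**What to change.** In Study Methods, state that:

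- the allocation sequence is generated in advance and concealed;
- the assignment is released only after the combined procedure is complete;
- patients whose trabectome is not performed are not randomised;
- the degrees ablated are recorded before the assignment is opened.

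Consent stays at the pre-op visit. No visits are added and the power calculation does not change. The 140 should then be counted as randomised patients, so slightly more than 140 may need to be consented. The main downside is that the post-operative drop prescription cannot be finalised before surgery.

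The change protects the operation only. Patients will still know their arm, and later follow-up and IOP assessment remain unmasked.

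### Beyond stops for side effects, no pilocarpine use is planned to be recorded and the per-protocol set is undefined, so that analysis can remove only some non-users

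*Combined protocol and SAP*

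**What the plan says.** **Treatment.** Study Methods gives the active arm as "The treatment group will receive post-operative treatment with pilocarpine 2% for 1 month postoperatively, in addition to the standard post-operative surgical drops". For the other arm, "The control group will receive the usual post-operative drop schedule without pilocarpine". No section states a dosing frequency.

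**Analysis.** The Analytic Plan puts all analyses on an ITT footing. Non-inferiority is declared if the upper 95% confidence limit for pilocarpine minus no pilocarpine, in percent IOP decrease at 1 year, is below 5%. It then adds: "Since the ITT approach can be anti-conservative in non-inferiority trials, a per-protocol analysis will also be performed". The per-protocol set is not defined anywhere.

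**What will be recorded.** Study Methods lists visual acuity, IOP and gonioscopy at follow-up visits. The Data and Safety Monitoring Policy adds a side-effect review at every visit; if a side effect is intolerable or unsafe, the drug is stopped and the patient's participation ends. Key Question 5 asks "What is the rate of pilocarpine related side effects and drug discontinuation due to adverse effects". A count of drops before and after surgery is a secondary outcome. Study Methods gives it no time point, and Key Question 3 sets it at 6 months and later.

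**Expected use.** The Background says: "Due to its frequent dosing requirement and large number of ocular and systemic side effects, pilocarpine has largely fallen out of favor". The Consent section says: "As no placebo will be utilized, patients will not be blinded to which group they are in".

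**The concern.** If some patients assigned to pilocarpine do not use it, or some controls receive it, the arms become more alike. The difference shrinks toward zero, and in a non-inferiority trial that favours the conclusion being sought. The plan recognises this and offers the per-protocol analysis as the counterweight.

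That analysis works only if non-users can be identified. The plan itself gives reasons to expect under-use: a demanding schedule, side effects and open-label assignment. Study Methods also says that most surgeons performing this operation do use pilocarpine, so use by a control patient is conceivable. Yet the only planned record that bears directly on use during the first month is stopping for side effects. A patient who quietly uses little or none stays in the per-protocol set. Without a stated frequency there is also no regimen against which to judge adherence. Month-1 use that is never recorded cannot be supplied by the analyst afterwards.

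**Working it through.** **Inputs from the documents** (Sample size considerations, Analytic Plan): 70 per arm, SD 7.5%, margin 5%, one-sided error 2.5%, assumed true difference 0, stated power above 95%.

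**Step 1. The plan's own figure.**
SE = 7.5 × √(2/70) = 1.268 points.
Power = Φ(5/1.268 − 1.96) = Φ(1.984) = 97.6% (97.5% with the t distribution). The stated power is confirmed and is not in question here.

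**Step 2. Assumptions not in the documents.** The full-use effect of pilocarpine is exactly 5 points. A share f of the pilocarpine arm uses none and gets no effect; the rest use it fully. Non-use is unrelated to outcome. The SD stays at 7.5%. The documents give no value for f, so a range is shown.

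**Step 3. No non-user identified.**
Expected difference = 5(1 − f).
P(declare) = Φ([5 − 5(1 − f)]/1.268 − 1.96) = Φ(5f/1.268 − 1.96).
For f = 0.20: Φ(1/1.268 − 1.96) = Φ(−1.171) = 12.1%.

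**Step 4. Half of the non-users identified and removed**, for example known stops for side effects.
Pilocarpine arm left: 70(1 − f/2). Non-user share left: g = (f/2)/(1 − f/2). SE = 7.5 × √(1/70 + 1/[70(1 − f/2)]). P(declare) = Φ(5g/SE − 1.96).
For f = 0.20: 63 patients remain, g = 0.111, the expected difference is 4.44, SE = 1.303, and Φ(0.556/1.303 − 1.96) = 6.3%.

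| Non-users f | None identified | Half identified | All identified |
|---|---|---|---|
| 0% | 2.5% | 2.5% | 2.5% |
| 10% | 5.9% | 4.0% | 2.5% |
| 20% | 12.1% | 6.3% | 2.5% |
| 30% | 21.9% | 9.8% | 2.5% |

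**Step 5. Sensitivity to the assumed effect.** If the full-use effect is 6 points and no non-user is identified, the figures are 1.1%, 3.6% and 9.2% at 10%, 20% and 30% non-use. At 7.5 points all three are below 2%. The table therefore shows the boundary case.

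**Step 6. Can the planned data identify non-users?**
- Stops for side effects: yes, through Key Question 5 and the safety review.
- Silent under-use or non-use: no planned item.
- Pilocarpine given to a control patient: no planned item.
- Drop counts: the time points in Key Question 3 all fall after the 1-month course ends, and they count drops needed to reach goal IOP. The Study Methods entry has no time point and does not say whether study pilocarpine counts.

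**The case against.** **Some use data are planned.** A reader might infer that use goes entirely unrecorded and that the per-protocol analysis can remove nobody. The documents do not support that: stops for side effects are to be captured, and side effects are one of the reasons that the Background gives for pilocarpine's decline. This objection stands, and it limits the point to non-use outside those stops.

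**The two analyses may differ.** A reader might also infer that the per-protocol result would be about as diluted as ITT. That is not shown. If half of the non-users are removed, 12.1% falls to 6.3%. How far the analyses differ also depends on whether patients terminated for side effects keep contributing data, which the documents leave open.

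**The figures concern a different quantity.** The primary analysis compares assigned strategies. If that difference, with use as it really occurs, is 4 points, concluding that it is below 5 is correct. This stands: the percentages are errors only for the full-use effect, and they do not show that the primary test exceeds 2.5%.

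**Charts may hold the information.** There is one provider and visits are routine, so prescriptions or medication histories may be on file. It would go too far to say that exposure could never be reconstructed at 1 year; the documents are silent. But possible chart notes are not a plan to collect use, and a prescription does not show use.

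**Adherence-based exclusion can itself bias.** It removes patients after randomisation, mainly from one arm, for reasons that may relate to outcome. This stands and belongs among the costs of the remedy.

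**Conclusion.** The point holds in limited form. The plan names a per-protocol analysis as its safeguard against dilution, but it neither defines the set nor collects first-month use beyond stops for side effects. As written, the safeguard can remove only some non-users, and no planned item detects pilocarpine use in the control arm.

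The size is unknown because the documents give no non-use rate. The illustration runs from 4.0% (10% non-use, half identified) to 21.9% (30% non-use, none identified), against a nominal 2.5%. It rests on a full-use effect exactly at the margin and on all-or-nothing non-use unrelated to outcome; larger effects give smaller figures. The stated power and the ITT comparison are unaffected. This is a worthwhile, inexpensive improvement rather than a flaw that invalidates the trial.

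A related conflict needs resolving: the Data and Safety Monitoring Policy ends participation for patients stopped for side effects, while the Analytic Plan says that all analyses are ITT. Until the two are reconciled, it is unclear how the ITT and per-protocol sets differ.

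**What to change.** 1. At the routine visits in the first month, record in both arms whether pilocarpine was used since the last visit, use against the regimen prescribed, the stop date and reason, and any pilocarpine given to a control patient.
2. State the assigned dosing frequency in Study Methods so that adherence can be judged. The frequency is for the investigators to state; none is proposed here.
3. Define the per-protocol set from these records before the outcome data are analysed, with an adherence threshold chosen by the investigators.
4. Reconcile the termination rule in the Data and Safety Monitoring Policy with the ITT statement in the Analytic Plan, and make patients stopped for side effects identifiable in both analyses.

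**Cost.** A few form fields at visits already taking place, and a few sentences in the plan. Self-reported use is imperfect and the per-protocol set will be smaller. Because exclusions fall mainly in one arm, selection bias is possible, so the per-protocol result should be read alongside ITT and not in place of it.

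### The side-effect analysis falls under intent-to-treat with no exposed-patient denominator, so the incidence asked for in Objective 2 would be diluted by any patients who never start pilocarpine

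*Combined protocol and SAP*

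**What the plan says.** The Analytic Plan opens with a rule that has no exception: "All analyses will be based on the intent-to-treat approach (ITT". The same section places side effects under that rule by naming them as an example for the "chi-square test for categorical variables (e.g., occurrence of side effects, need for further surgery". Descriptive results are by arm: "Standard descriptive statistics will be used to summarize the baseline characteristics and outcomes of the two treatment arms".

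Only one other analysis set is mentioned, and its reason is the non-inferiority question: "Since the ITT approach can be anti-conservative in non-inferiority trials, a per-protocol analysis will also be performed". Its membership is not defined.

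Two items ask about the effects of taking the drug. Objective 2 is "To determine the incidence and characteristics of pilocarpine induced side effects in this population". Key Question 5 is "What is the rate of pilocarpine related side effects and drug discontinuation due to adverse effects".

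Study Methods sets the planned exposure. "The treatment group will receive post-operative treatment with pilocarpine 2% for 1 month postoperatively", while "The control group will receive the usual post-operative drop schedule without pilocarpine".

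The Data and Safety Monitoring Policy adds that a patient whose pilocarpine is stopped because a side effect is intolerable or unsafe also has their participation in the study ended.

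**The concern.** Intent-to-treat suits the comparison of the two allocation policies. It does not by itself suit a descriptive question about how often a drug causes harm in those who take it. A patient who never instils a drop can have neither a drug-induced effect nor a discontinuation, yet counts in the denominator under the stated rule.

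Objective 2 is one of only two objectives, and Risks and Benefits gives fewer side effects as the patient's gain from omitting pilocarpine. A diluted incidence would therefore understate the very quantity that motivates the control regimen.

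Non-initiation is plausible. The Consent section says patients will know their group and be told the drug's risks, and the Background describes frequent dosing and many side effects. The plan gives no rate and no expectation, and it does not call for recording whether the drug was ever used. Without that record, an exposed-patient denominator may not be recoverable later.

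**Working it through.** **The plan's own figure.** The only computable figure is the power of the primary comparison, and this point does not depend on it. With 70 per group, margin 5, SD 7.5 and one-sided 2.5%: SE = 7.5 × √(2/70) = 1.268; 5/1.268 = 3.944; 3.944 − 1.960 = 1.984; power = 97.6%. This agrees with the stated value of more than 95%. The plan gives no figure for side effects.

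**Inputs.** The pilocarpine arm has 70 patients (Sample size considerations). Three quantities are assumptions, because the documents give none of them:
- *r*, the incidence in patients who used the drug
- *b*, the incidence of the same complaints without it
- *a*, the share of the pilocarpine arm who never start

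**Formula.** Incidence by allocation = (1 − a) × r + a × b.

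**Results with r = 30%, b = 5%.**
- a = 0: 30.0%, no dilution
- a = 10% (7 of 70): 0.90 × 30 + 0.10 × 5 = 27.5%
- a = 20% (14 of 70): 0.80 × 30 + 0.20 × 5 = 25.0%

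**Results with b = 0.** The relative understatement equals *a*.
- 7 non-starters: true rates of 10%, 20% and 30% become 9%, 18% and 27%
- 14 non-starters: they become 8%, 16% and 24%
- 1 non-starter: 20% becomes 19.7%

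Discontinuation always follows the b = 0 case, since a patient who never starts cannot stop.

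**Against sampling error.** The standard error of a 30% incidence in 70 patients is √(0.30 × 0.70/70) = 5.5 points. The 2.5-point shift at 10% non-starters is under half of that, and the 5.0-point shift at 20% is about nine-tenths of it.

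**Control patients who use pilocarpine.** They do not enter the formula and cannot change the pilocarpine-arm incidence. They affect only the arm difference. With a = 10% and an assumed 5% of controls exposed, the control rate is 0.95 × 5 + 0.05 × 30 = 6.25%, and the difference is 27.5 − 6.25 = 21.25 points instead of 25.0.

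**Patients whose inclusion is ended.** The Analytic Plan keeps every randomised patient, while the monitoring policy ends inclusion for those stopped for side effects. The documents do not say whether their events are retained. As an illustration, suppose 30% of users have a side effect and 10% of users stop for it. If those who stop were removed altogether, the incidence would be (30 − 10)/(100 − 10) = 22.2%, and the discontinuation rate for adverse effects would be zero by construction. If they are retained, this loss does not occur.

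**The case against.** The strongest reply is that comparison by allocated arm is the right analysis of side effects. The benefit claimed for omitting pilocarpine is a contrast between two policies, and the randomised arms estimate it without confounding. The control arm also supplies the background rate needed before any complaint can be called drug-induced. All of this stands, and the between-arm comparison should remain the main one. Making users versus non-users the main comparison would exchange a possible dilution for confounding in an unblinded trial.

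It is also fair to say that the dilution is conditional and modest next to the standard error. That stands too. But the dilution is systematic, and a confidence interval computed on the wrong denominator does not reveal it.

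A reader might infer three stronger claims that the documents do not support:
- *The incidence is understated as a matter of fact.* This requires patients allocated to pilocarpine who never start, and no such number is given.
- *Control patients sit in the denominator.* Pooling over 140 would halve a 20% rate to 10%, but the plan summarises outcomes by arm and tests between arms.
- *Both planned sets bias the incidence downward.* The per-protocol set is undefined and is introduced for the non-inferiority question. If applied to side effects it might drop patients who stopped for them, which lowers the rate. It would probably also drop non-starters, which raises it. The net direction is not fixed.

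**Conclusion.** The point holds as a mismatch between the stated rule and the question. Intent-to-treat literally covers the side-effect analysis, and no denominator of exposed patients is defined for Objective 2 or Key Question 5. The effect is dilution in proportion to non-initiation. It is nil if everyone starts. Under assumed rates of 30% in users and 5% background, the incidence would read 27.5% with 10% non-starters and 25.0% with 20%. These figures rest wholly on assumed rates and show scale only.

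The between-arm comparison by allocation is valid and is not at fault. Separately, the rule ending study inclusion does not fit with intent-to-treat, and it bears on exactly the patients whose events Objective 2 counts. This is a clarification worth making before data collection ends, not a defect in the primary analysis.

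**What to change.** Amend the Analytic Plan along these lines:

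*Efficacy analyses, and the comparison of side effects between arms, will be by intent-to-treat; the between-arm comparison is the main side-effect comparison. In addition, the incidence of side effects and of discontinuation because of them (Objective 2, Key Question 5) will be reported with exact 95% confidence intervals among patients in the pilocarpine arm who used at least one dose. Any pilocarpine use in the control arm will be listed separately. The per-protocol set will not be used for side effects.*

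Record one yes/no item, any pilocarpine used, at the side-effect review already planned for each visit.

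Reconcile the Data and Safety Monitoring Policy with the intent-to-treat sentence, so that patients whose drug is stopped for side effects, and their events, remain in the side-effect analysis. This concerns which data are analysed, not when treatment should be stopped.

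The cost is a few sentences in the plan, one extra data item and one extra summary table.
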